The addition to the higher doses in the Q4W cohort with extended 12 week study duration (including 2 new visits at Week 10 and Week 12) for the open label dose-finding period will more appropriately ensure that steady state has been reached after 3 alirocumab injections (2 interdose intervals) in terms of PK and LDL-C and related parameter reduction efficacy. An intermediate visit between the dosing interval (Week 10) is specifically introduced to better document the PK and LDL-C data from the Q4W dosing regimen that is known to show some peak-trough variability over the 4-week dosing interval, ie, a peak in the decrease at the mid dosing interval time point and trough reduction in LDL-C at the end of dosing interval time period. Thus, extending the duration of a higher Q4W dosing regimen to 12 weeks (an additional 4 weeks) will secure more comprehensively data on the LDL-C related profile reduction potential of a Q4W dosing regimen for alirocumab.

Given the 12 week duration, only LDL-C and key related parameters (TC, non-HDL-C, and TG) will be measured at Week 10 and Week 12 to minimize blood collection. The post-treatment follow-up period is no longer needed based on the data collected from the previous 3 cohorts.

All patients in Cohort 4 will receive alirocumab at 150 mg Q4W for BW <50 mg/300 mg Q4W for BW \geq 50 kg using prefilled syringes.

Cohort 4, similar to the other cohorts, will include alirocumab administration during the open-label extension that will continue until approximately 10 weeks before the initiation of the pediatric phase 3 study or December 2018 at the latest. The patients, after a wash-out period of at least 10 weeks after the last injection of alirocumab, will have the opportunity to participate in the phase 3 study. Though Cohorts 1 to 3 will be switched to the optimal regimen selected for the phase 3 study, Cohort 4 will remain on their initial regimen given the planned study end date of December 2018.

Conclusion on the benefit risk assessment with alirocumab:

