For Cohort 4, sterile alirocumab drug product will be supplied at a concentration of 150 mg/mL as 1 mL volume in a prefilled syringe (PFS).

For Cohort 4: The study treatment is a single SC injection of 1 mL for 150 mg dose of alirocumab and 2 injections of 1 mL containing 150 mg each to provide a total 300 mg dose (2 mL) of alirocumab through PFS, administered every 4 weeks in the abdomen, thigh, or outer area of the upper arm. Study drug will be administered by SC injection Q4W, starting at Week 12 and continuing up to the last injection, 4 weeks before the end of the open-label extension period.

Dosing for the open-label extension treatment period should ideally be administered Q2W SC or Q4W SC at approximately the same time of the day; however, it is acceptable to have a treatment window of ± 3 days. The time of day is based on the patient's preference.

Alirocumab administration will continue until at least 10 weeks before the initiation of the pediatric Phase 3 study in the site where the patient is potentially participating or December 2018, whichever comes first.

In the event an injection is delayed by more than 7 days or is completely missed, the patient should return to the original schedule of study drug dosing without administering additional injections. If the delay is less than or equal to 7 days from the missed date, the patient should administer the delayed injection and then resume the original dosing schedule.

Detailed instructions for transport, storage, preparation, and administration of IMP will be provided by the site to the patient/caregiver.

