10 STUDY PROCEDURES

For all visits after Day 1/Week 0 (inclusion visit), a timeframe of a certain number of days will be allowed. The window period for all visits until Week 8 is ± 3 days and for the follow-up period and Visits 9 and 10 it is ± 7 days. During the open label extension period, the visit window is ± 14 days for Visits 11 onward, and ± 7 days for the end of treatment visit and the end of OLE visit.

For all visits after Day 1/inclusion visit, if one visit date is changed, then the next visit should take place according to the original schedule as outlined in [Section 1.3](#) and [Section 1.4](#).

Blood samplings:

The blood sampling for determination of lipid parameters (ie, total-C, LDL-C, HDL-C, TG, non-HDL-C, Apo B, Apo A-1, ratio Apo B/Apo A-1, Lp [a]) should be performed in the morning, in fasting condition (ie, overnight, at least 8 hours fast and refrain from smoking) for all site visits throughout the study. Blood sampling for adrenal gland, pituitary and gonadal hormones should be obtained in the morning and at the same time if possible. Alcohol consumption within 48 hours and intense physical exercise within 24 hours preceding the blood sampling are discouraged.

Note: if the patient is not in fasting conditions, the blood sample will not be collected and a new appointment will be given the day after (or as close as possible to this date) to the patient with instruction to be fasted (see above conditions).

Laboratory tests:

The laboratory data are collected in accordance with the study schedule in [Section 1.3](#) and [Section 1.4](#), and forwarded to the central laboratory:

- Hematology - complete blood cell count including hematocrit, hemoglobin, red blood cell count, white blood cell count with differential count and platelets.
- Chemistry - glucose, sodium, potassium, chloride, bicarbonate, calcium, phosphorus, urea nitrogen, creatinine, uric acid, lactate dehydrogenase, total protein, albumin and gamma GT. Note: eGFR and creatinine clearance will be calculated at screening; creatinine clearance will be calculated for all subsequent visits where chemistry lab testing is performed.
- Lipid panel 1: TC, calculated LDL-C, HDL-C, TG, non-HDL-C.
- Lipid panel 2: Apo B, Apo A-1, ratio Apo B/Apo A-1, and Lp(a).
- Liver panel: ALT, AST, ALP (alkaline phosphatase) and total bilirubin (in case of total bilirubin values above the normal range, differentiation into conjugated and non-conjugated bilirubin will occur automatically).

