11 STATISTICAL CONSIDERATIONS

11.1 DETERMINATION OF SAMPLE SIZE

No power sample size calculations were performed for the main phase. A sample size of 10 patients per cohort is empirical and based on the sample size of the Phase 1 studies (R727-CL-904 and R727-CL-1001) conducted in adults. No less than 4 patients with BW <50 kg and no less than 4 patients with BW \geq 50 kg will be enrolled in 4 independent cohorts (Cohort 1, Cohort 2, Cohort 3, and Cohort 4), which will allow the evaluation of the pharmacokinetics/pharmacodynamics (PK/PD) profile and safety of different alirocumab doses/dose regimen in each BW category and to compare with PK/PD profile and safety observed in adult patients.

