2.1.3 Efficacy endpoints

Efficacy parameters include lipid parameters (ie, Total-C, calculated LDL-C, measured LDL-C, HDL-C, TGs, non-HDL-C, Apo B, Apo A-1, ratio Apo B/Apo A-1, Lp (a)). All these parameters are measured or calculated by a Central Laboratory, for both scheduled and unscheduled time points. Calculated LDL-C is obtained using the Friedewald formula. Non-HDL-C is calculated by subtracting HDL-C from the Total-C. If TG values exceed 400 mg/dL (4.52 mmol/L), the LDL-C should be measured by the Central Laboratory (via beta quantification method) rather than calculated. All measured LDL-C values provided by the Central Laboratory will not be used for the analysis of calculated LDL-C endpoints.

Unless otherwise specified, all lipid values (scheduled or unscheduled, fasting or not fasting) may be used to provide a value for the efficacy endpoints. All measurements, scheduled or unscheduled, fasting or not fasting, will be assigned to analysis windows defined in [Section 2.5.4](#) [Table 3](#) and [Table 4](#) in order to provide an assessment for time points when the lipid values were to be collected as per protocol. For TGs, only fasting measurements will be used. Measurements with missing fasting status will be excluded from the analyses.

For all time points post baseline, the value used for the analyses at a given time point is the value obtained within the corresponding analysis window.

The baseline value is defined as the last available value obtained up to the date and time of the first OLDFI IMP administration. For patients included and not treated, the baseline value is defined as the last available value obtained up to the date and time of inclusion.

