The binary endpoint at time point of interest will be derived from observed and imputed lipid values at this time point. Combined estimates for proportion of patients reaching the target for each alirocumab dose groups and for each cohort will be obtained through the SAS MIANALYZE procedure.

2.4.4.2.4 *Summary of results per time point*

For the open-label dose finding treatment period, central laboratory values (in conventional (US) and international units), percent change from baseline, and/or when appropriate absolute change from baseline (in conventional and international units), for calculated LDL-C, Total-C, HDL-C, fasting TG, and non HDL-C at each time point (including Week 10 and W12 time points for Cohort 4), for Lp(a), Apo-B, Apo-A1 and ratio Apo-B/Apo-A1 (absolute change from baseline) at Week 8 time points will be summarized in the mITT population using:

- For lipids other than TG and Lp(a): LS mean and SE for each alirocumab dose group, obtained from the same MMRM models as used for endpoints above and including planned time points (see [Section 2.4.4.2.1](#)) and with raw values, changes from baseline, or percent change from baseline as response variable in the model as appropriate.
- For TG and Lp(a): mean and SE for each alirocumab dose group obtained from multiple imputation approach followed by the robust regression models as used for endpoints above and including planned time points (see [Section 2.4.4.2.2](#)) and with raw values or percent changes from baseline as response variable in the model as appropriate.

In addition, quantitative descriptive summaries by time point (value at visit and % change from baseline) will be presented for all lipids using observed (ie, non-missing) data.

The time profile in %change from baseline of each parameter (except ratio ApoB/Apo A-1 where absolute change will be used) will be plotted according to alirocumab dose received by using LS mean and SE except for TGs and Lp(a). For these 2 parameters, the combined estimate for mean and SE will be used.

For OLDFI /OLE combined period, only quantitative descriptive summaries by time point during the OLDFI/OLE combined efficacy treatment period will be presented for all lipids using observed data in the mITT population. Lipid results pre- versus post-switch to the selected Phase 3 doses will be analyzed separately for Cohorts 1 to 3.

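### From Visit 11 of the extension, LDL-C on Q4W dosing may be sampled anywhere in the dosing interval, and the SAP's time-point summaries ignore days since injection

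*Protocol*

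**What the plan says.** **Visit timing.** Protocol Section 10 keeps visits up to Week 8 within ±3 days. It then relaxes this: "During the open label extension period, the visit window is ± 14 days for Visits 11 onward". The end-of-OLE visit is ±7 days.

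**Injection timing.** Protocol Section 8.1 gives extension injections their own limit: "it is acceptable to have a treatment window of ± 3 days". Section 10.1.4.1 allows Q4W injections at the site or at home. Section 8.1.2 has same-day clinic dosing follow sampling, which says nothing about samples drawn on other days.

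**Known pattern.** The Cohort 4 rationale (Protocol Section 4) describes Q4W LDL-C as "known to show some peak-trough variability over the 4-week dosing interval", with the largest decrease in mid-interval and the smallest at the end.

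**Analysis.** Under SAP 2.1.3, "the value used for the analyses at a given time point is the value obtained within the corresponding analysis window". SAP 2.5.4 (Table 4) sets most extension windows at target day -28 to +27 and takes the value nearest the target study day, counted from the first injection. For the combined period, SAP 2.4.4.2.4 states that "only quantitative descriptive summaries by time point during the OLDFI/OLE combined efficacy treatment period will be presented for all lipids using observed data". Days since injection do not enter. For drug concentration they do: SAP 2.1.5 and Table 5 define a Q4W trough as 22 to 35 days after the previous injection and drop samples whose previous injection date is unknown.

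**The concern.** Time since injection is, on the protocol's own account, a determinant of measured LDL-C on Q4W dosing. The main phase controls it closely and the extension from Visit 11 does not. If visits drift off the injection day, a row of time points from Week 8 onwards mixes trough values with values from elsewhere in the interval, and the reader cannot tell which.

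A sampling artefact could then be read as a change in, or good maintenance of, the Q4W effect. Long-term efficacy in the extension is a listed endpoint (Protocol Section 9.4.4). Whether Q4W holds LDL-C down over the whole interval is also the issue that the Cohort 3 results raised.

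**Working it through.** **1. The plan's own figure.** Table 4 rule: target = 7 × week + 1, window = target - 28 to target + 27. Week 130: 7 × 130 + 1 = 911, window 883 to 938, which matches Table 4. The window is 56 days, or two Q4W intervals.

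**2. Nominal position in the interval.** Extension dosing starts at Week 14 (Cohort 3) or Week 12 (Cohort 4).
- Cohort 4, Weeks 24, 36 and 48: 12, 24 and 36 weeks later, all multiples of 4, so trough.
- Cohort 3, Weeks 26 to 110 and Week 130: also multiples of 4, so trough.
- Cohort 3, Week 120: 106 weeks later, remainder 2, so mid-interval by schedule. The SAP dates first enrolment in the study to 29-Sep-2016. Adding 840 days gives 17 January 2019, after the December 2018 end date, so this visit should not be reached.

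**3. Permitted range.** At Week 8 on Q4W, injection and visit may each move ±3 days, giving 28 ± 6 = 22 to 34 days. From Visit 11, with injections on schedule, a visit d days from the nominal day is 28 + d days after the last injection for d ≤ 0 and d days after it for d > 0. With d from -14 to +14 this covers days 1 to 28. Only d = -6 to 0 gives 22 days or more: 7 of 29 permitted days, or 24%. If a late visit also holds back the injection, the sample can reach 28 + 14 = 42 days.

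**4. Size (assumptions).** The documents give no peak-trough gap and no distribution of visit days. I assume a gap G of 10 to 30 points and a symmetric triangular profile: share of G = 1 - |days - 14|/14, and zero beyond day 28. With visits uniform and injections on schedule, the shares over the 29 days sum to 15, so the mean is 15/29 = 52% of G. Simulation with injections uniform over ±3 days and visit offsets truncated at ±14 days gives:

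| Visit-day spread | Samples at 22-35 days | Mean share of G | G = 10 | G = 30 |
|---|---|---|---|---|
| SD 3 | 52% | 19% | 1.9 | 5.8 |
| SD 5 | 42% | 29% | 2.9 | 8.8 |
| SD 7 | 36% | 37% | 3.7 | 11.1 |
| Uniform | 24% | 51% | 5.1 | 15.3 |

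These gains are in percentage points against a day-28 trough. Week 8 carries a little of the same effect: with both offsets uniform over ±3 days, the mean earliness is (49 - 1)/(3 × 7)/2 = 1.14 days, and 1.14/14 = 8% of G. Read against Week 8, each gain is therefore about 0.8 to 2.4 points smaller.

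**The case against.** **Little may be exposed.** This stands. Cohort 4 is the only cohort sure to stay on Q4W. Its extension flowchart (Protocol 1.4.2) schedules injections at the Week 24 and Week 36 lipid visits, and footnote d places them at the site. Where sampling precedes the injection at that visit and the dosing window is kept, the sample is a trough. The SAP plans first Cohort 4 enrolment for 01-May-2018, so Week 24 falls on 16 October 2018 and Week 36 on 8 January 2019. That leaves roughly one ±14-day visit for about 10 patients, some of whom may go straight to Phase 3. Cohort 3 may switch dose, and the SAP reports its lipids before and after the switch separately. Protection of Cohort 4 is not complete, because Sections 8.1.2 and 10.1.4.1 also foresee home or self-injection.

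**A reader might infer that the SAP averages everything in a 56-day window and compares it with Week 8, or Q4W with Q2W.** It does neither. It takes one value per patient, nearest a nominal trough day, and plans descriptive summaries with no such contrast. The risk lies in how adjacent time points are read.

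**A reader might infer a one-way bias of up to 23 points.** That figure gives all of the 76% non-trough days the full 30-point gap (0.76 × 30 = 22.8), including days 1 to 3, when on the assumed profile LDL-C is still near trough. Overdue injections also push the other way.

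**Durability is studied elsewhere.** The Cohort 4 main phase does this at Weeks 8, 10 and 12 with its own model. Combined lipid analyses are exploratory at the first two analysis steps (SAP Section 3). The final combined analysis is not so labelled.

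**Conclusion.** The gap is real but modest. The plan lets a compliant Q4W lipid sample from Visit 11 fall anywhere in the interval, and summarises it without the one variable that would show this. Under a symmetric profile and an assumed 10 to 30 point gap, the apparent gain is about 2 to 6 points at a visit-day SD of 3 days. It rises to about 5 to 15 points if visits are uniform over the window. It is near nil where the injection follows sampling at the same site visit, and it reverses where an injection is overdue. The true size is unknown, since both the gap and the visit-day spread are assumptions.

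The documents do not support extending this to the primary Week 8 endpoint, whose samples are held to 22 to 34 days, or to Phase 3 dose selection, which SAP Section 3 bases on the main-phase efficacy analyses. It is a low-priority improvement to a descriptive extension summary.

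**What to change.** In SAP 2.4.4.2.4:

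- Derive days since the previous injection for each extension lipid sample, and report its distribution by time point.
- For patients on a Q4W regimen, add a trough-only LDL-C summary (value and percent change) beside the all-sample one, using the SAP's existing 22 to 35 day interval. Samples beyond 35 days then appear only in the all-sample row and the timing table.
- State that the trough-only row is the one to use in any descriptive reading of the extension against Week 8.
- Use a listing where numbers are very small.

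The cost is one derived variable and some SAP text. Injection dates are already recorded in the eCRF or diary (Protocol 8.7.1). No visit, dose or blood sample changes. The drawback is small row counts.

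Two sets of protocol passages bear on sample timing and must be reconciled: the place of Cohort 4 extension injections (footnote d of 1.4.2 against 8.1.2 and 10.1.4.1), and the handling of delayed injections (8.1 uses 7 days without distinguishing cohorts; 8.1.2 uses 14 days for Cohorts 3 and 4).

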10.1 VISITS SCHEDULE

10.1.1 Screening period

Only patients who meet/are likely to meet the inclusion criteria as noted in Section 7.1 should be screened. The screening period (including run in) will take place up to 6 (+1) weeks or 42 (+7) days (and as short as possible, upon receipt of laboratory eligibility criteria) prior to inclusion/Day 1 visit, and may include more than one site visit for patients for whom not all screening procedures can be done at the first visit. The screening visit can take place from 42 (+7) days before the inclusion visit (for patients without a stable background LMT [optimal statin dose \pm other LMTs or non-statin LMTs if statin intolerant] for at least 4 weeks prior to the screening visit and/or patients suspected of being heFH but without a confirmed diagnosis and consenting to undergo the centralized genotyping) up to 14 (-7) days before the inclusion visit (for patients with a stable LMT background therapy [optimal-statin dosing \pm other LMT] for at least 4 weeks prior to the screening visit and confirmed diagnosis of heFH. Not all screening assessments and procedures need to be done at the same visit. The sample for lipid testing must be obtained only after the patient has been on a stable LMT therapy (optimal statin dose \pm other LMT) for at least 4 weeks.

During the screening period the following procedures should be followed:

Visit 1 (Week -6 (+1) to Week -2 (-1)) at clinical site:

- Complete informed consent - the patient and their parents will receive complete information about the study both verbally and in writing. Written informed consent for the study must be obtained prior to any study related investigations.

- Complete informed consent for genetic testing for patient electing to undergo genotyping for heFH and/or for use of previous documented genotyping. Written informed consent for the study must be obtained prior to genotyping consent and sampling.
- Contact IVRS/IWRS for notification of screening. Patient number will be allocated by the IVRS/IWRS. This patient number is composed of a 12-digit number containing the 3-digit country code, the 4-digit center code and the 5-digit patient chronological number (the 5-digit patient chronological number is 00001 for the first patient screened in a center, 00002 for the second patient screened in the same center).
- Assess inclusion/exclusion criteria.
- Obtain patient demography – age, gender, race, and ethnicity.
- Obtain medical history, surgical history, alcohol habits and smoking habits for adolescents.
- Obtain family medical history (including risk factors relating to premature CHD, see [Appendix F: Simon Broome Register Diagnostic Criteria for heFH](#)), allergy.
- Document prior medication history within the previous 12 weeks, especially for lipid modifying therapy (including statin) and nutraceutical products that may affect lipids (eg, omega-3 fatty acids, plant stanols such as found in Benecol, flax seed oil, psyllium).
- Record concomitant medications.
- Check stability of background LMT.
- Get body weight and height measurements.
- Get Tanner stage measurement by the same investigator/designee at each visit if possible.
- Perform physical examination. Take vital signs including HR and BP.
- Genotyping if patient consents to undergo centralized genotyping for heFH (Note: Buccal swab, saliva, or blood sample needed; if blood sample is drawn for genotyping only, the patient does not need to be fasting).
- Collect AEs from this point onward:
 - All AEs and SAEs will be collected from the time of informed consent signature and throughout the study until the post study treatment follow-up visit.
- Obtain fasting blood sample for:
 - Lipid panel 1: total-C, calculated LDL-C, HDL-C, TG, non-HDL-C,
 - Lipid panel 2: Apo B, Apo A-1, ratio Apo B/Apo A-1, and Lp(a),
 - Hematology: red blood cell count including hematocrit, hemoglobin, WBC count with differential count and platelets,
 - Chemistry: glucose, sodium, potassium, chloride, bicarbonate, calcium, phosphorous, urea nitrogen, creatinine, uric acid, total protein, LDH, albumin, and γ GT,
 - Liver panel (ALT, AST, ALP, and total bilirubin),
 - CPK,
 - Pregnancy test (blood test) for females who have experienced menarche.

- An appointment will be given for the next visit.
- Give instruction on diet: Patients will be instructed to follow a diet in accordance with the American Academy of Pediatrics guidelines (1) or equivalent throughout the entire study (ie, both phases).
- Give instruction on stable background LMT: Patients will be instructed to be treated with stable optimal dose of statin ± other LMT for at least 4 weeks, if not already on stable optimal dosing for at least 4 weeks, or to continue the LMTs at the same dose.

Note: All patients will be qualified for inclusion based on the confirmation of heFH diagnosis by genotyping or clinical criteria, stable dose of LMT (including statin at optimal dose, unless intolerant) for at least 4 weeks prior to the screening visit, and by the LDL-C value obtained during the screening period, on stable dose of statins ± other LMTs after at least 4 weeks.

All patients who successfully screen for Cohort 1 and are not included in Cohort 1, due to the appropriate Cohort 1 weight group being fully enrolled, may participate to Cohort 2 but only after eligibility, including safety assessments, is reconfirmed. Patients who are successfully screened for Cohort 2 but are not enrolled, due to the appropriate Cohort 2 weight group being fully enrolled, may participate in Cohort 3 without the need to repeat the run-in/screening period if there is no more than 3 months between eligibility confirmation and inclusion. In such a circumstance, the run-in/screening period from Cohort 2 will substitute for the run-in/screening period for Cohort 3. If there is more than 3 months between initial screening and planned enrollment in Cohort 3, patient eligibility, including safety assessments, must be reconfirmed.

Safety and eligibility assessments noted above include all lab tests listed as exclusionary, based on specified results.

Patients should be instructed to follow a diet in accordance with the American Academy of Pediatrics (AAP) guidelines (1) or equivalent throughout the entire study (ie, both phases). The dietitian or site staff with appropriate training will review the patient's diet at the screening visit and periodically throughout the study.

